12.1 Cytogenetics and Molecular Genetics

DNA will be extracted from participant's blood samples. See Figure 2 for amounts and vials required. DNA (EDTA sample) will be stored on patients for future genetic disease association studies. These future studies will look whether genetic polymorphism within patients, particularly within a region of the DNA called the Human Leukocyte Antigen (HLA) system, are linked to different clinical outcomes.

13 Trial procedures

Follow up assessments will place take place at weeks 2, 4, 6, 8, and 10, and then at months 3, 4, 5, 6, 7, 8, 9, 10, 11, and 12, 24, 36, and 48 post randomisation. All patients will complete the 2 weeks and 3 months follow up. The number of fortnightly assessments completed will depend on when they reach the primary endpoint and the number of monthly follow ups completed when they are recruited (see section 13.2 for time point cut-offs for assessments). Data collection be completed 3 months after the last patient is recruited.

Along with the main trial, there will be a mechanistic study looking at the role of glycosylation of the IgG Fc region. Samples will be taken at baseline and 2 weeks and then compared to samples from healthy volunteers who have undergone a lumbar puncture for non-inflammatory conditions. The CSF samples from healthy volunteers will be requested from the Walton Research CSF biobank. The biobank is managed by the Walton Centre NHS Foundation Trust, has full ethical approval from Wales REC4 and all samples are kept under the Human Tissue Authority License. The biobank request will be made independent of this trial and protocol. Full details of the mechanistic study can be found in section 19.

13.1 Assessments

Screening:

During the screening, participants will undergo a clinical assessment, MRI or CT scan using local site standard scanning protocols, lumbar puncture, and blood samples as part of the standard diagnostic procedures to determine if the patient has suspected autoimmune encephalitis and if they meet all the inclusion criteria and none of the exclusion criteria. If patients are eligible they are consented, randomised and treatment will be started within 5 days.

2 week follow up:

Clinical assessment will be repeated at 2 weeks (±2 days), post randomisation. Blood samples will be repeated at 2 weeks. Section 12 for details on blood samples.

Clinical assessment:

- Adverse events
- HDU/ITU admission
- Seizure incidences
- Use of ventilator support
- Time to hospital discharge
- Use of further treatment
- Clinically defined relapse
- Mortality

GOSE assessments will occur fortnightly (± 2 days) for the first 3 months post randomisation, and then monthly (± 7 days) up to 12 months post randomisation. Once a participant has scored a 5 or greater on the GOSE for two assessments in a row participants will be considered as having reached the primary end point and the regular GOSE assessments will stop. All participants will still complete the GOSE at 3 months post randomisation even if they have achieved recovery. The GOSE will be completed at 12, 24, 36, and 48 months post randomisation for those participants who reach those time points.

Patients will have the option of completing the GOSE online, or via the telephone. Telephone help can be provided to those completing it online if necessary. Automated alerts will be set up to help patients complete the GOSE in the right time window, and to inform the study team if this appears not to be happening. If patients are still in hospital during GOSE assessments the study team and/or study partner will assist the patient to complete the assessment at the bedside, taking into account the assessments of allied health professionals such as occupational therapy and physiotherapy where necessary. Once patients are discharged from hospital, they and their study partner will receive a reminder on the day before the GOSE follow up window starts and a reminder on the first day of the

follow up window, that the GOSE should be completed. If the GOSE is not completed on the correct day, the trial team will receive a notification and they will attempt to contact the participant by phone for 4 days (for fortnightly assessments) or 6 days (for monthly assessments), or until the assessment is completed.

3 Months:

Clinical assessment, the GOSE, and blood samples will all be repeated at 3 months (±7 days). Participants will also be asked to complete the EQ5D5L and the EBIQ.

12 Months:

Clinical assessment, the GOSE, EQ5D5L, and the EBIQ will all be repeated at 12 months (±7 days). Patients will also complete a battery of functional assessments, and neuropsychological and cognitive tests. The Neuropsychological and cognitive tests will be administered by an appropriately trained and supervised psychologist. In some sites this will be by the local clinical neuropsychology team but the central trial team will have a roving assistant psychologist who will be able to administer the relevant tests at sites where it is not possible for the local team to administer them.

Functional Outcome Assessments:

- Modified Rankin Score: Developed for the assessment of disability and dependence following stroke and widely used as an outcome measure within neurological infections and noninfectious encephalitis.
- Barthel Index: An ordinal scale used to measure activities of daily living and assesses the
 ability of an individual to care for him/herself. It has been used in patients with neurological
 disorders and brain injury.
- Liverpool Outcome Score: developed for the assessment of outcome following Japanese Encephalitis. It was designed for use in adolescents and adults as well as having been used in the ENCEPH UK study.

Neuropsychology and Cognitive Testing:

- Addenbrooke's Cognitive Examination III: measures cognitive impairment
- Wechsler Memory Scale version IV: measures different aspects of memory functions in adults.
 Assessment will include auditory memory index, Visual memory index, immediate memory index, and delayed memory index.
- Wechsler Adult Intelligence (WAIS) test version IV: measures intelligence and cognitive ability
 in adults. The sub-scales administered will be the Processing Speed Index and the working
 memory index.

- Confrontational Naming Task: task taken from the language module of the Neuropsychology
 Assessment Battery. Assesses wording finding ability.
- Trail Making Test Parts A and B: Used to assess higher executive function
- **Test of Premorbid Functioning**: Assesses an individual's cognitive and memory functioning prior to onset of condition.
- Beck Depression Inventory: Self report measure of the severity of a patient's depression
- Beck Anxiety Inventory: Self report measure of the severity of a patient's anxiety
- **Perceived Deficits Questionnaire:** a self-report questionnaire measuring the perception of cognitive dysfunction.

	Visits (insert visit numbers as appropriate)									
Procedures	Screening (as part of Standard of care)	Baseline	Treatment Phase	2 week follow up	Week 4-10	3 month follow up	Month 4-11	12 month Follow Up	Months 24-48	As required
Eligibility assessment	X									
Brain Imagining Scan (CT or MRI scan)	Х									
CSF Samples	Х			Х						
Informed consent		Х								
Demographics		Х								
Medical history		Х								
Physical examination		Х								
Vital signs		Х	Х	Х		Х		Х		
Concomitant medications		Х								Х
Randomisation		Х								
Dispensing of trial drugs		Х	Х							
Blood Samples		Х		Х		Х				
Laboratory tests	Х	Х		Х		Х				
Compliance			Х							
Use of further immunotherapy			Х	Х		Х		Х		
Adverse event assessments			Х	Х		Х				
Clinical assessment		Х		Х		Х		Х		

	Visits (insert visit numbers as appropriate)										
Procedures	Screening (as part of Standard of care)	Baseline	Treatment Phase	2 week follow up	Week 4-10	3 month follow up	Month 4-11	12 month Follow Up	Months 24-48	As required	
Glasgow Outcome Scale Extended		Х		Х	Х	Х	Х	Х	Х		
EQ5D5L						Х		Х	Х		
EBIQ						Х		Х	Х		
Modified Rankin Scale								Х			
Liverpool Outcome Score								Х			
Barthel Index								Х			
Addenbrooke's Cognitive Examination III								Х			
Wechsler Memory Scale Version IV								Х			
WAIS Version IV: Processing Speed Index								Х			
WAIS Version IV: Working Memory Index								Х			
Confrontational Naming task (from Neuropsychology Assessment Battery)								Х			
Trial Making Test Part A and B								Х			
Premorbid Cognitive Ability (TOPF)								х			

		Visits (insert visit numbers as appropriate)								
Procedures	Screening (as part of Standard of care)	Baseline	Treatment Phase	2 week follow up	Week 4-10	3 month follow up	Month 4-11	12 month Follow Up	Months 24-48	As required
Beck Depression Inventory								X		
Beck Anxiety Inventory								Х		
Perceived Deficits Questionnaire								Х		

13.2 Follow-up

Data collection will continue for all patients until 3 months after the last patient is recruited. The primary outcome measure will be collected fortnightly for the first 3 months for all participants, and then monthly until 12 months post-randomisation for a subset of participants, unless participant reaches primary endpoint. A subset of participants will also complete the GOSE annually until the end of the trial. Clinical follow up assessments and assessments of self-rated health will be completed at 3 month for all participants, and then at 12 months and annually for a subset of participants. Participants recruited after month 45 of recruitment, will complete all assessments up to and including the 3 month assessment. Patients recruited up until month 44 of recruitment will complete all assessments up to and including the 12 month assessment, patients recruited up until month 32 of recruitment will complete all assessments up to and including the 36 month assessment. Those patients recruited up to month 8 of recruitment will complete all assessments up to and including the 48 month assessment. A detailed schedule of the assessments can be found in figure 3 in section 13.1.

For the fortnightly assessments, the follow up window is ±2 days. Participants will be notified 1 day before the follow up window starts and then again on the first day of the follow up window. If the participant does not complete the assessment on the first day, they will be contacted every day until they complete the assessment or the follow up window closes. For the monthly assessment, the follow up window is ±7 days. The same procedure will be used, except if participant doesn't complete the assessment on day 1 of the follow up window, they will be contacted every other day until the window closes. Any assessments that require in person attendance must be scheduled within the appropriate follow up window. Participants will be contacted at each assessment time point regardless of whether they completed the previous assessment point unless they withdraw their consent to take part in that section of the trial or the trial as a whole.

14 Internal pilot and recruitment rates

We have included Stop/Go decision points based on initiating the study at 10 months, and recruitment progress. Recruitment progress will be assessed by the number of patients recruited at 6, 12, 18 and 24 months following the commencement of recruitment and the length of time it takes to recruit the first 50 patients for the internal pilot. We will use a traffic light system to indicate progression onto the

remainder of the trial, where GREEN = Proceed with no modification; AMBER = review progress and reasons for failure to meet target; instigate remedial action, and set new target in conjunction with the Trial Steering Committee (TSC), Independent Data Monitoring Committee (IDMC) and Efficacy and Mechanistic Evaluation (EME) Board; RED = Proceed only with major modifications, following discussion and approval from with TSC, IDMC and EME. If two successive review points are RED then this would indicate that the project would automatically stop.

14.1 Internal Pilot

Figure 4 Stop/Go Decision Time Points

Outcome domain	Metric	GREEN	AMBER	RED
Progress with Set Up	Assessment at 10 months after study started	Ready to open first site Ethics approved MHRA Approval HRA approval R&D approval of 1st site	Contracts signed Ethics submitted MHRA Submitted HRA Submitted	Contracts not signed and Ethics, MHRA, HRA not submitted
Recruitment	No. of patients 6 months after recruitment starts (target 2; study month 16)	>1	0-1	-
Recruitment	No. of patients 12 months after start (target 14; study month 22)	>11	7-11	<7
Recruitment	No. of patients 18 months after start (target 35; study month 28)	>28	7-28	<17
Recruitment	No. of patients 24 months after start (target 70; study month 34)	>56	35-56	<35
Recruitment for internal pilot	Time from start of patient recruitment (and start of study) to recruit first 50 patients	21 (30) months	21-26 (30-35) months	> 26 (35) months
Retention	Percentage of randomised patients remaining in the study for primary outcome	> 90%	75-90%	< 75%
Adherence	Percentage of patients commencing treatment within 5 days of randomisation	> 90%	75-90%	< 75%
Contamination	Percentage of patients randomised to placebo arm who receive IVIG within the first 14 days post-randomisation	< 5%	5-10%	> 10%

The statistical analysis of the internal pilot data from the placebo arm will be conducted and reported during the closed session of the IDMC by a statistician not otherwise involved in the trial. The internal pilot will look at retention, adherence, and contamination (see figure 4 for definition). Internal pilot findings which do not present outcomes by trial arm will be presented to the TMG and TSC but otherwise communication regarding other internal pilot outcomes will be provided via recommendations from the IDMC to the TSC.

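### In Figure 4 the 18-month recruitment row classes 7 to 16 recruits as both AMBER and RED, and any two successive REDs among the dated recruitment reviews must include that row

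*Protocol*

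**What the plan says.** Section 14 of the protocol sets a traffic-light rule for progression. The two lower colours carry different actions:

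- AMBER: "AMBER = review progress and reasons for failure to meet target; instigate remedial action, and set new target in conjunction with" the steering committee, the data monitoring committee and the funder's board.
- RED: "RED = Proceed only with major modifications, following discussion and approval from with TSC, IDMC and EME".

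It then adds: "If two successive review points are RED then this would indicate that the project would automatically stop".

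The bands are in Figure 4, section 14.1. For the row "No. of patients 18 months after start (target 35; study month 28") they are GREEN >28, AMBER 7-28 and RED <17. The rows on either side are "No. of patients 12 months after start (target 14; study month 22"), with >11, 7-11 and <7, and "No. of patients 24 months after start (target 70; study month 34"), with >56, 35-56 and <35. The row "No. of patients 6 months after recruitment starts (target 2; study month 16") has GREEN >1, AMBER 0-1 and a dash under RED.

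A further row, "Time from start of patient recruitment (and start of study) to recruit first 50 patients", gives 21 (30) months under GREEN, 21-26 (30-35) under AMBER and >26 (35) under RED. Section 27 refers back to section 14 for all criteria, and no other section restates the 18-month bands.

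**The concern.** A traffic-light rule works only if each count has one colour. In the 18-month row the AMBER band starts well below the RED cut-off, so a range of counts has two colours and two sets of consequences. AMBER leads to review, remedial action and a new target. RED requires major modifications with approval, and counts towards the two-successive-REDs rule.

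The range lies where a slow trial would land, at under half of target. If it is left alone, the committees and funder would have to choose the colour after seeing the count, which is what pre-set criteria are meant to prevent.

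**Working it through.** **Inputs.** All come from Figure 4, section 14.1.

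| Review | Target | GREEN | AMBER | RED |
|---|---|---|---|---|
| 6 months | 2 | >1 | 0-1 | none |
| 12 months | 14 | >11 | 7-11 | <7 |
| 18 months | 35 | >28 | 7-28 | <17 |
| 24 months | 70 | >56 | 35-56 | <35 |

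**Step 1: overlaps and gaps.** Each whole-number count was classified against the three bands of its row.

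- 12 months: no overlap, no gap.
- 24 months: no overlap, no gap.
- 18 months: AMBER needs a count from 7 to 28 and RED needs 16 or fewer. Both hold for 7, 8, ..., 16, which is 16 - 7 + 1 = 10 counts. As shares of target these run from 7/35 = 20% to 16/35 = 46%. RED covers 0 to 16, or 17 counts, so 10 of the 17 RED counts are also AMBER. There is no gap.

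**Step 2: which cell is off the pattern.** Each cut-off is divided by its target.

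- GREEN: 11/14 = 79%, 28/35 = 80%, 56/70 = 80%.
- RED: 7/14 = 50%, 17/35 = 49%, 35/70 = 50%. (Half of 35 is 17.5, so 17 is that figure rounded down.)
- Lower end of AMBER: 7/14 = 50%, 7/35 = 20%, 35/70 = 50%.

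At 18 months the GREEN and RED cut-offs fit the neighbouring rows. Only the lower end of AMBER does not.

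**Step 3: candidate corrections.** AMBER 17-28 with RED <17 leaves no overlap and no gap, and restores the pattern. RED <7 with AMBER 7-28 also removes the overlap, but puts the RED boundary at 20% of target, unlike the 12- and 24-month rows.

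**Step 4: effect on the stop rule.** Section 27 lists five stop/go points: study month 10, then 6, 12, 18 and 24 months of recruitment. The 6-month point cannot be RED, which rules out the pairs (study month 10, 6 months) and (6, 12 months). The pairs left are (12, 18) and (18, 24), and both include the 18-month review. Take 6 recruits at month 12, which is RED, and 12 at month 18. Under the RED column this is a second successive RED and indicates a stop. Under the AMBER column it leads to remedial action and a new target.

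**Step 5: the 50-patient row.** Study month minus recruitment month is 16 - 6 = 22 - 12 = 28 - 18 = 34 - 24 = 10 in the four dated rows. In the 50-patient row it is 30 - 21 = 35 - 26 = 9. Straight-line interpolation between the targets of 35 at month 18 and 70 at month 24 reaches 50 at 18 + 6 × (50 - 35)/(70 - 35) = 20.6 months. This fits the stated recruitment month of 21 and points to the bracketed study months as the figures to check. As printed, GREEN is given as 21 with no inequality sign and AMBER begins at 21, so that boundary is not cleanly divided either.

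**The case against.** The intended band can be read off the table. GREEN >28 and RED <17 leave only 17-28 between them, and a committee would probably settle on that. The error touches no estimand, analysis, type I error, power or safety provision. All of this stands, and it makes the correction easy. It does not remove the need for one, because the printed AMBER cell still supports the other colour for anyone who wants the trial to continue.

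A reader might infer that any count from 7 to 16 at month 18 decides whether the trial stops. The document does not support that. The rule needs two successive REDs, so the colour at month 18 matters for stopping only if the month-12 or month-24 review is also RED.

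A reader might also infer that the stop is mechanical. Section 14 says that two REDs would indicate an automatic stop, while section 16.6 describes early termination as the funder's assessment of feasibility with input from the two committees. People would therefore be reading the table when the question arose. Neither section says which colour applies to 7 to 16.

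The table was read from a PDF by a program. A lost digit (17 read as 7) cannot be excluded, nor can a lost inequality sign in the 50-patient row. How the 7 arose is not known, and the point does not depend on it.

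The one-month difference in offset might reflect a counting convention, and the row is defined first by time from the start of recruitment. No materially different decision has been shown to follow from it.

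**Conclusion.** As printed, the 18-month row is wrong: 10 counts, 7 to 16, are both AMBER and RED. It is a faulty decision threshold with real consequences, because the two colours lead to different actions and every pair of successive REDs among the dated recruitment reviews includes this row. The cell most likely at fault is the lower end of AMBER. That inference rests on the roughly 80% and 50% of target used in the 12- and 24-month rows, and on the digit being absent from the source document and not only from the text as read.

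The statement about pairs of REDs is limited to the dated reviews. The 50-patient, retention, adherence and contamination rows also have RED bands, and the protocol does not say whether they count as review points for the two-REDs rule.

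The mismatch of 9 against 10 months in the 50-patient row is correct arithmetic but minor.

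**What to change.** Check the 18-month row against the source document. If it reads the same there, change AMBER to 17-28 and leave GREEN >28 and RED <17 as they are.

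In the 50-patient row, reconcile the bracketed study months with the other rows. With the 10-month offset they would be 21 + 10 = 31 and 26 + 10 = 36. Write the bands so that 21 months falls in one colour only, for example GREEN <21, AMBER 21-26 and RED >26.

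The cost is a correction to one table, notified to the steering committee, the data monitoring committee and the funder. Sample size, data collection and analysis are unaffected. It should be made before the 18-month count is known.

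### Figure 4's 18-month recruitment row labels 7–16 patients both AMBER and RED, so the automatic-stop rule has no single answer there

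*Protocol*

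**What the plan says.** Section 14 of the protocol defines the colours and their consequences. For AMBER: "AMBER = review progress and reasons for failure to meet target; instigate remedial action, and set new target". For RED: "RED = Proceed only with major modifications, following discussion and approval from with TSC, IDMC and EME". It then adds: "If two successive review points are RED then this would indicate that the project would automatically stop".

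Section 14.1 (Figure 4) supplies the recruitment thresholds. The 18-month row, whose metric is "No. of patients 18 months after start (target 35; study month 28"), reads "target 35; study month 28) >28 7-28 <17", that is, GREEN above 28, AMBER 7–28 and RED below 17. The 12-month row (target 14) has GREEN above 11, AMBER 7–11 and RED below 7. The 24-month row (target 70) has GREEN above 56, AMBER 35–56 and RED below 35. The 6-month row has no RED band. No section gives an order of precedence for a count that meets two bands.

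**The concern.** A stop/go rule is useful only if each possible result leads to one decision fixed in advance. In the 18-month row the AMBER and RED bands overlap, so for part of the range the colour depends on which column is read.

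The two colours lead to different actions: remedial steps and a new target under AMBER, or continuation only with major modifications and approval under RED. A RED also counts towards the automatic stop. Because RED is impossible at 6 months, months 12 and 18 are the first pair of recruitment reviews that can trigger that stop. If the month-18 count falls in the overlap, the label would have to be chosen after the count is known, by bodies with an interest in the answer.

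**Working it through.** **Inputs** (Protocol Section 14.1, Figure 4)

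| Review | Target | GREEN | AMBER | RED |
|---|---|---|---|---|
| 12 months | 14 | >11 | 7–11 | <7 |
| 18 months | 35 | >28 | 7–28 | <17 |
| 24 months | 70 | >56 | 35–56 | <35 |

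**Step 1: label every whole-number count.** At 12 and 24 months each count falls in exactly one band, with no overlap and no gap. At 18 months the counts 7, 8, …, 16 satisfy both AMBER (7–28) and RED (<17): 16 − 7 + 1 = 10 counts with two labels. There is no gap.

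**Step 2: compare the limits with the targets.**

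| Review | 50% of target | 80% of target | Printed RED limit | Printed AMBER lower limit | Printed GREEN limit |
|---|---|---|---|---|---|
| 12 months | 7 | 11.2 | <7 | 7 | >11 |
| 18 months | 17.5 | 28 | <17 | **7** | >28 |
| 24 months | 35 | 56 | <35 | 35 | >56 |

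The 50%/80% pattern reproduces every limit (rounding 11.2 and 17.5 down) except the 18-month AMBER lower limit. That limit is 7/35 = 20% of target and equals the 12-month AMBER lower limit.

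**Step 3: follow the consequences through the stop rule.**

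- 5 patients at month 12 (RED), then 14 at month 18. Read as RED, there are two successive REDs and the project stops. Read as AMBER, it continues with remedial action.
- 8 at month 12 (AMBER), 14 at month 18, 30 at month 24 (RED). Read as RED at month 18, the project stops at month 24. Read as AMBER, it does not.
- 12 at month 12 (GREEN), 15 at month 18, 40 at month 24 (AMBER). No automatic stop on either reading, but the action required at month 18 still differs.

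**Step 4: how often the overlap would be met.** The protocol gives no forecast of shortfall, so this step rests on an assumption: recruitment is Poisson at a fraction f of target, with independent increments. Then N12 ~ Poisson(14f) and N18 − N12 ~ Poisson(35f − 14f), so N18 has mean 35f. The two quantities are P(7 ≤ N18 ≤ 16) and P(N12 < 7 and 7 ≤ N18 ≤ 16).

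| Fraction of target | Two labels at month 18 | RED at month 12, then two labels at month 18 |
|---|---|---|
| 30% | 0.86 | 0.75 |
| 40% | 0.74 | 0.58 |
| 45% | 0.59 | 0.43 |
| 50% | 0.42 | 0.30 |
| 60% | 0.16 | 0.11 |
| 80% | 0.010 | 0.006 |
| 100% | about 0 | about 0 |

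The last column leaves out the second route to an ambiguous stop: not RED at month 12, two labels at month 18, RED at month 24. Between 30% and 50% of target that route adds about 0.09 to 0.16.

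**Step 5: test the correction.** With AMBER 17–28, GREEN >28 and RED <17, every 18-month count has exactly one label.

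**The case against.** Several points can be made on the other side.

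- **The month-18 count alone never stops the trial.** A RED at month 12 or month 24 is also needed; otherwise the conflict is only between the AMBER and RED actions. Both actions go to the same bodies (TSC, IDMC and the EME Board). This is correct and limits the consequence, but the action required at month 18 remains undefined.
- **Termination is partly a matter of judgement.** Section 16.6 describes early termination as the funder's assessment of feasibility, with TSC and IDMC input, so a misprinted cell is unlikely to end the trial unnoticed. That is fair, but Section 16.6 does not say which label applies, and Section 14 still calls the stop automatic.
- **The probabilities matter only if recruitment is poor.** They fade above about 60% of target, as the table shows. This stands, although poor recruitment is the situation the rule was written for.
- **The value 17 is inferred.** Half of 35 is 17.5, so a strict 50% rule would give AMBER 18–28 and RED below 18. That would mean changing the RED cell as well. Starting AMBER at 17 keeps the printed RED limit and alters only the cell that breaks the pattern. The sponsor should confirm the intended value.
- **It is an evident slip that does not touch the analysis.** It has no bearing on the primary endpoint, the model, the sample size or participant safety. That affects how much weight to give it, not whether it is an error.

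**Conclusion.** The error is real and exact: ten counts, 7 to 16, carry two labels at the 18-month review, and the protocol does not resolve them. This follows from the printed limits alone. When month 12 or month 24 is also RED, the choice of label decides whether the project stops. In all other cases it decides which action month 18 requires.

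The probabilities are illustrative. They depend on the Poisson assumption and on recruitment well below target, and run from 0.75 at 30% of target to 0.30 at 50% for the month 12–18 route. Whether the 7 is a dropped digit or was carried over from the row above cannot be settled from the document, but the row's own RED and GREEN limits and the neighbouring rows all point to that cell.

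**What to change.** In Figure 4, 18-month row, change AMBER from 7–28 to 17–28 and leave GREEN (above 28) and RED (below 17) as they are. The sponsor should first check the cell against the source table and confirm that 17 is the intended limit, with the TSC, IDMC and EME Board informed because they act on these bands.

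The cost is one table cell in the next protocol amendment. It should be corrected before the 18-month count is known, so that the label cannot be chosen in the light of the result.
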